10.6.1 Occurrence of Adverse Events

For AEs reported during the observation period, the incidence will be tabulated by type, time of onset, seriousness, and causal relationship to Leuplin PRO. In addition, events listed as the safety specifications for the surveillance in “2. Summary of Pharmacovigilance Plan” in the risk management plan will be tabulated separately.

10.6.2 Factors that May Affect the Safety

For ADRs reported during the observation period, the incidence will be tabulated by patient background factors (e.g., disease status, presence or absence of concurrent renal impairment, presence or absence of concurrent hepatic impairment) and treatment status of Leuplin PRO.

11.0 Posting of Surveillance Information

Surveillance information will be posted on the following open website before starting the surveillance:

- Japan Pharmaceutical Information Center-Clinical Trials Information

14.0 Other Necessary Matters

14.1 Revision of the Protocol

During the surveillance, attention will be paid to comprehend the status of progression of the surveillance, presence or absence of ADRs that are unexpected based on the precautions/serious ADRs, presence or absence of increased incidence of certain ADRs, and appropriateness of surveillance items, and this protocol will be reviewed and revised if necessary. If partial change to dosage and administration or indications is approved during the surveillance, the necessity of revising the protocol will be discussed if necessary, and the protocol will be revised as needed.

14.2 Actions to be Taken for Problems and Questions

If any safety problem is detected, data will be carefully examined to discuss measures.

Appendix Observation schedule

| Surveillance item | Time point of surveillance | Observation period | |
|----------------------------------|--|---|---------------------------|
| | | After 24 weeks or at discontinuation of observation | At the start of treatment |
| Patient registration | At patient registration | ○ | |
| | Date of administration of Leuplin PRO | ○ | |
| | Patient identification number | ○ | |
| | Patient initials | ○ | |
| | Date of birth | ○ | |
| Patient baseline characteristics | Assessment based on the exclusion criteria | ○ | |
| | Time of diagnosis of prostate cancer | | ○ |
| | ECOG Performance Status | | ○ |
| | Disease status | | ○ |
| | Diagnostic category | | ○ |
| | Predisposition to hypersensitivity | | ○ |
| | Concurrent illness | | ○ |
| | History of thromboembolism | | ○ |
| | Height, body weight | | ○ |
| Treatment given | Treatment status of prostate cancer drug immediately before the start of Leuplin PRO treatment | | ○ |
| | Treatment status of Leuplin PRO | ← ○ → | |
| Adverse event | Treatment status of prostate cancer drug other than Leuplin PRO | ← ○ → | |
| | Injection site reaction | ← ○ → | |
| | Adverse event other than injection site reaction | ← ○ → | |

○ : Performed

← ○ →: Performed throughout the period

1.1 List of Terms and Abbreviations

- Leuplin PRO: Leuplin PRO for Injection Kit 22.5 mg is abbreviated as Leuplin PRO.
- Adverse drug reaction (ADR), etc.: ADR, etc. is an abbreviation of ADR/infection. ADRs, etc. refer to all adverse events (AEs) other than those assessed by the investigator to be not related to Leuplin PRO. In this document, “adverse drug reactions/infections” is used in titles, and “ADRs, etc.” is used in the text and tables.
- Serious adverse event (SAE): A SAE is an adverse event assessed by the investigator to be serious. Events included in the MedDRA code list in Takeda Medically Significant AE List will be handled as serious even if assessed by the investigator to be not serious.
- Causal relationship: An event assessed as not related to Leuplin PRO will be handled as “not related.” Events not unrelated to Leuplin PRO in the text and tables refer to all events other than those assessed as not related to Leuplin PRO.
- Summary statistics: Collective term for number of patients, mean, standard deviation, maximum, minimum, and quartiles
- Patient with no CRF collected: Enrolled patient for whom the CRF has not been collected
- Patient with the CRF collected: Enrolled patient for whom the CRF has been collected
- Finalized patient: Patient for whom the CRF has been collected and finalized at least once by data lock point
- Non-finalized patient: Patient for whom the CRF has been collected, but has not been finalized by data lock point
- Age: If the month and day of starting Leuplin PRO treatment is smaller than the month and day of birth, age will be calculated as year of starting Leuplin PRO treatment - year of birth - 1. If the month and day of starting Leuplin PRO treatment is equal to or greater than the month and day of birth, age will be calculated as year of starting Leuplin PRO treatment - year of birth. If the day of birth is unknown, 1 will be used for calculation.
- Time from diagnosis of prostate cancer to patient registration (months):
 - Actual number (units: month) = (“date of patient registration” - “date of diagnosis” + 1)/30.44
- BMI (kg/m^2): Calculated as body weight (kg)/height (m)² (displayed to one decimal place by rounding)

- Induration: AE with “induration” selected for “Specific symptom (multiple answers allowed)” in the column of [Adverse event: Injection site reaction] in the CRF
- Prostate cancer drug other than luteinizing hormone-releasing hormone (LH-RH) agonists or antagonists
 - Bicalutamide: Drugs with a NHI drug code starting with 4291009
 - Flutamide: Drugs with a NHI drug code starting with 4291005
 - Other: Other drugs not listed above

1.2 Analysis Sets

The analysis set in this surveillance is safety population. This analysis set is defined as described below.

- Safety population

In this document, the safety population is defined as all Leuplin PRO-treated patients evaluable for safety with no major protocol violation. Patients for whom the CRF has been collected will be excluded from the safety population if any of the following criteria is met:

- Not treated with Leuplin PRO
- Treatment before the contract period
- Registration 15 days or more after Leuplin PRO treatment
- It is unknown whether the patient experienced an AE

1.3 Number of Digits to be Displayed

- Percentage (%)

Proportion of patients with an AE or an ADR, etc. or number of AE or ADR, etc.:

 Displayed to two decimal places by rounding

Other:

 Displayed to one decimal place by rounding

- Summary statistics

Mean, median, first quartile, and third quartile:

 Displayed to one lower digit than raw data by rounding

Standard deviation:

 Displayed to two lower digits than raw data by rounding

Minimum and maximum:

 Displayed to the same number of digits as the relevant data

1.4 Important Identified Risks, Important Potential Risks, and Important Missing Information

- Important identified risks
 - Injection site reaction: Injection site reaction is defined as the following AEs:
 - HLT code 10022097 [Infusion site reactions]
 - HLT code 10057196 [Administration site reactions NEC]
 - PT code: Refer to [Attached table PTs corresponding to risks].
 - Decreased bone mass density: Decreased bone mass density is defined as the following AEs:
 - SMQ code 20000178 [Osteoporosis/osteopenia (SMQ) narrow]
 - PT code: Refer to [Attached table PTs corresponding to risks].
 - Diabetes mellitus: Diabetes mellitus is defined as the following AEs:
 - SMQ code 20000041 [Hyperglycemia/new onset diabetes mellitus (SMQ) broad]
 - Interstitial lung disease : Interstitial lung disease is defined as the following AEs:
 - SMQ code 20000042 [Interstitial lung disease (SMQ) narrow]
 - Depression: Depression is defined as the following AEs:
 - SMQ code 20000167 [Depression (excl suicide and self injury) (SMQ) narrow]
 - SMQ code 20000037 [Suicide/self-injury (SMQ) narrow]
 - Thromboembolism: Thromboembolism is defined as the following AEs:
 - SMQ code 20000004 [Cardiac failure (SMQ) narrow]
 - SMQ code 20000166 [Conditions associated with central nervous system haemorrhages and cerebrovascular accidents (SMQ) narrow]
 - SMQ code 20000064 [Haemorrhagic cerebrovascular conditions (SMQ) narrow]
 - SMQ code 20000063 [Ischemic central nervous system vascular conditions (SMQ) narrow]
 - SMQ code 20000165 [Cerebrovascular disorders, not specified as haemorrhagic or ischaemic (SMQ) narrow]
 - SMQ code 20000082 [Emolic and thrombotic events, arterial (SMQ) narrow]
 - SMQ code 20000084 [Emolic and thrombotic events, venous (SMQ) narrow]
 - SMQ code 20000083 [Emolic and thrombotic events, vessel type unspecified and mixed arterial and venous (SMQ) narrow]
 - SMQ code 20000047 [Myocardial infarction (SMQ) broad]
 - SMQ code 20000168 [Other ischaemic heart disease (SMQ) broad]

- Pituitary apoplexy: Pituitary apoplexy is defined as the following AEs:
 - PT code: Refer to [Attached table PTs corresponding to risks].
- Hepatic dysfunction/jaundice: Hepatic dysfunction/jaundice is defined as the following AEs:
 - SMQ code 20000009 [Cholestasis and jaundice of hepatic origin (SMQ) narrow]
 - SMQ code 20000013 [Hepatic failure, fibrosis, and cirrhosis and other liver damage-related conditions (SMQ) narrow]
 - SMQ code 20000010 [Hepatitis, non-infectious (SMQ) narrow]
 - SMQ code 20000008 [Liver related investigations, signs and symptoms (SMQ) narrow]
- Cardiac failure: Cardiac failure is defined as the following AEs:
 - SMQ code 20000004 [Cardiac failure (SMQ) narrow]
- Urinary tract obstruction: Urinary tract obstruction is defined as the following AEs:
 - PT code: Refer to [Attached table PTs corresponding to risks].
- Important potential risks
 - Anaphylaxis: Anaphylaxis is defined as the following AEs:
 - SMQ code 20000021 [Anaphylactic reaction (SMQ) narrow]
 - SMQ code 20000071 [Anaphylactic/anaphylactoid shock conditions (SMQ) narrow]
 - Hypertension: Hypertension is defined as the following AEs:
 - SMQ code 20000147 [Hypertension (SMQ) narrow]
- Important missing information: Not applicable

1.5 Other Handling

- Time of onset of AE (or ADR, etc.): Time of onset of AE (or ADR, etc.) will be calculated as date of onset of AE (or ADR, etc.) - start date of Leuplin PRO treatment + 1. If the day of AE (or ADR, etc.) is unknown, 1 will be used for calculation. If an AE (or ADR, etc.) occurs in the same year and month as Leuplin PRO treatment is started, the start date of Leuplin PRO treatment will be used for calculation.

2 Number of Surveillance Medical Institutions, Number of Enrolled Patients, and Patient Composition

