3.2 Rationale

To evaluate potential effects of differences between Leuplin PRO and Leuplin SR, that is, difference amounts of leuprorelin acetate administered in a single dose and different time profiles of serum drug concentration after administration, on the safety, it was decided to investigate the occurrence of injection site reaction and other adverse drug reactions (ADRs) with an incidence of 1% or higher, including the time of onset, incidence, and seriousness.

The sample size of 300 patients was determined to detect ADRs with an incidence of 1% or higher at a probability of 95% or higher.

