9.4 Adverse Events (AEs)

1) Surveillance items

Presence or absence of injection site reaction, details of injection site reaction (specific symptom, date of onset, seriousness and reason for seriousness [refer to Table 2], cause of discontinuation of Leuplin PRO treatment, intervention (presence or absence and contents), date of outcome assessment, outcome, causal relationship to Leuplin PRO [refer to Table 3]).

Presence or absence of AE other than injection site reaction (refer to Table 1), AE term, date of onset, seriousness and reason for seriousness (refer to Table 2), cause of discontinuation of Leuplin PRO treatment, intervention (presence or absence and name of the drug/intervention), date of outcome assessment, outcome, causal relationship to Leuplin PRO* (refer to Table 3)

Patients with “not resolved” or “unknown” outcome or “unevaluable” causal relationship should be followed up wherever possible.

* For the causal relationship to Leuplin PRO, the rationale for “not related” and the reason for “unevaluable” shall be collected.

Note) Additional points to consider for AEs

Abnormal worsening of target disease, for instance, worsening beyond the expected natural course of the disease, will be handled as an AE.

2) Time points of surveillance

Period from the start of Leuplin PRO treatment to 24 weeks after the start of treatment (or discontinuation of observation)

Table 1 Definition of adverse events

An AE is defined as any untoward medical occurrence in a clinical investigation subject administered a drug; it does not necessarily have to have a causal relationship with this treatment. An AE can therefore be any unfavorable or unintended sign (e.g., abnormal laboratory finding), symptom, or disease temporally associated with the use of a drug, whether or not it is considered related to the drug.

The following are also handled as AEs:

- Symptoms and so forth that occur in infants breast-fed by their mothers under treatment with a drug
- Untoward symptoms and so forth that occur in children treated with a drug
- Symptoms and so forth that occur as a result of occupational exposure to a drug
- Symptoms and so forth that occur after administration of counterfeit medicines of our ethical drugs
- Untoward symptoms that have become known to occur in drug users through lawsuits or other legal actions

Table 2 Criteria for assessing seriousness

An AE satisfying any of the following is assessed as serious:

1. Results in death (death)

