5.2.1 Occurrence of Adverse Events by Seriousness, Time of Onset, and Outcome

Patients included Safety population

in analysis:

Analysis item: AEs

Stratification Total

factors: Seriousness [Serious, not serious]

Time of onset [<7 days, $7-28$ days, $28-56$ days,
 $56-84$ days, $84-168$ days, >168 days]

Outcome [Recovered, recovering, not recovered,
recovered with sequelae, died,
unknown, unknown]

Analysis For the aforementioned analysis item, analysis will be performed in each stratum methods: of the stratification factor as described below.

- (1) Number of patients with an AE
- (2) Number of AE
- (3) Proportion of patients with an AE
- (4) Type of AE

For each analysis, events or patients will be counted as described below.

[Number of patients with an AE]

- Number of patients who experienced an AE

[Number of AE]

- Number of reported AE. Multiple episodes of the same AE in the same patient will be tabulated as the total number of episodes.

[Proportion of patients with an AE]

- The proportion of patients with an AE will be calculated as number of patients with an AE/number of patients included in safety evaluation $\times 100$.

[Type of AE]

- AEs will be coded using the MedDRA/J. AEs will be classified by SOC and then tabulated by PT. For the SOC of investigations, AEs will be sorted by HLGT (lined up in ascending order of HLGT code, but not output) and then tabulated by PT.
- For SOC, the number and proportion of patients with an AE will be listed in internationally agreed SOC order. Multiple episodes of the same SOC in the

same patient will be counted as 1 patient for the relevant SOC. Multiple episodes of the same SOC will be employed as 1 event according to the order of precedence described at the end.

- For PT, the number and proportion of patients with an AE will be listed in ascending order of PT code. Multiple episodes of the same PT in the same patient will be counted as 1 patient for the relevant PT. Multiple episodes of the same PT will be employed as 1 event according to the following order of precedence:

Seriousness: serious → not serious

Time of onset: <7 days → 7-<28 days → 28-<56 days → 56-<84 days → 84-<168 days → >=168 days

Outcome: died → recovered with sequelae → not recovered → recovering → recovered → unknown

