5.2.2 Occurrence of Adverse Drug Reactions/Infections by Seriousness, Time of Onset, and Outcome

Patients included Safety population

in analysis:

Analysis item: ADRs, etc.

Stratification Total

factors: Seriousness [Serious, not serious]

Time of onset [<7 days, 7-<28 days, 28-<56 days,
56-<84 days, 84-<168 days, >=168
days]

Outcome [Recovered, recovering, not recovered,
recovered with sequelae, died,
unknown, unknown]

Analysis For the aforementioned analysis item, analysis will be performed in each stratum
methods: of the stratification factor as described below.

- (1) Number of patients with an ADR, etc.
- (2) Number of ADR, etc.
- (3) Incidence of ADR, etc.
- (4) Type of ADR, etc.

For each analysis, events or patients will be counted as described below.

[Number of patients with an ADR, etc.]

- Number of patients who experienced an ADR, etc.

[Number of ADR, etc.]

- Number of reported ADR, etc. Multiple episodes of the same ADR, etc. in the same patient will be tabulated as the total number of episodes.

[Incidence of ADR, etc.]

- The incidence of ADR, etc. will be calculated as number of patients with an ADR, etc./number of patients included in safety evaluation $\times 100$.

[Type of ADR, etc.]

- ADRs, etc. will be coded using the MedDRA/J. ADRs, etc. will be classified by SOC and then tabulated by PT. For the SOC of investigations, ADRs, etc. will be sorted by HLGT (lined up in ascending order of HLGT code, but not output) and then tabulated by PT.
- For SOC, the number and incidence of ADR, etc. will be listed in internationally agreed SOC order. Multiple episodes of the same SOC in the same patient will be counted as 1 patient for the relevant SOC. Multiple episodes of the same SOC will be employed as 1 event according to the order of precedence described at the end.
- For PT, the number and incidence of ADR, etc. will be listed in ascending order of PT code. Multiple episodes of the same PT in the same patient will be counted as 1 patient for the relevant PT. Multiple episodes of the same PT will be employed as 1 event according to the following order of precedence:

Seriousness: serious \rightarrow not serious

Time of onset: <7 days \rightarrow 7-<28 days \rightarrow 28-<56 days \rightarrow 56-<84 days \rightarrow 84-<168 days \rightarrow ≥ 168 days

Outcome: died \rightarrow recovered with sequelae \rightarrow not recovered \rightarrow recovering \rightarrow recovered \rightarrow unknown

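### SAP 1.5 omits the day-unknown condition from its same-month onset rule, so read literally it replaces known onset dates with the injection date

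*SAP*

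**What the plan says.** SAP 1.5 (Other Handling) handles time of onset in three steps.

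1. The general formula is "date of onset of AE (or ADR, etc.) - start date of Leuplin PRO treatment + 1", so the injection day is day 1.
2. A missing day is imputed: "If the day of AE (or ADR, etc.) is unknown, 1 will be used for calculation".
3. For any event "in the same year and month as Leuplin PRO treatment is started, the start date of Leuplin PRO treatment will be used for calculation".

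Step 2 carries its own condition, that the day is unknown. Step 3 opens with a different condition, the calendar month, and does not mention an unknown day. The birth-date rule in SAP 1.1 does state that condition: "If the day of birth is unknown, 1 will be used for calculation".

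The result feeds the onset bands of SAP 5.2.1 and 5.2.2, for example "Time of onset [<7 days, 7-<28 days, 28-<56 days". Protocol 9.4 collects an onset date for each event ("AE term, date of onset, seriousness and reason for seriousness"). Protocol 3.2 lists onset timing among the things to be investigated: "including the time of onset, incidence, and seriousness".

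**The concern.** Two programmers can apply step 3 differently and produce different onset tables from the same data. One infers that it covers only unknown days and leaves every recorded date alone. The other follows the text and overwrites every recorded date in the injection month.

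The literal error runs one way: events can only move into the <7 day band. Nothing later reverses it, because repeat episodes of a PT in one patient are assigned to the earliest band ("Time of onset: <7 days → 7-<28 days → 28-<56 days"). How many dates are overwritten depends on the calendar day of injection, which has nothing to do with the drug. This matters because the surveillance exists partly to examine a different serum concentration profile over time, so early versus later onset is a result readers will look at.

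**Working it through.** **Plan's own figure.** The documents give none on this point. The sample size of 300 does not enter.

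**Inputs.** The onset formula and the two substitution rules come from SAP 1.5. The bands come from SAP 5.2.1 and 5.2.2. The registration window, April 2016 to 31 March 2017, comes from Protocol 8.0. The documents give neither the distribution of injection dates nor an onset profile, so both are assumed where marked.

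**Why step 3 exists.** Take an injection on 20 October and an October event with unknown day. Step 2 alone gives 1 − 20 + 1 = −18, an onset before treatment. This happens unless the injection is on the 1st of a month. Over the 365 dates from 1 April 2016 to 31 March 2017 there are 12 firsts, so (365 − 12)/365 = 353/365 = 96.7% of injection dates are affected. Step 3 repairs this, which is good evidence of its intent.

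**What it does to a known date.** Injection 3 October, onset 28 October, day recorded:
- by the formula: 28 − 3 + 1 = day 26, band 7-<28;
- by the literal step 3: 3 − 3 + 1 = day 1, band <7.

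In the extreme case, injection on 1 June with onset on 28 June, the true day is 28 (band 28-<56) and the literal result is again day 1.

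**Calendar count, no onset profile assumed (30-day month).** Onset days 7 to 27 are 6 to 26 days after injection, which is 21 dates. The number still in the injection month, and therefore reset, is:

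| Injection on | Dates reset, of 21 |
|---|---|
| 1st | 21 |
| 10th | 15 (16th to 30th) |
| 15th | 10 (21st to 30th) |
| 20th | 5 (26th to 30th) |
| 25th | 0 |

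**Share reset by true onset day (assumes injection dates equally likely over the 365 days).** Day 7: 293/365 = 80%. Day 14: 209/365 = 57%. Day 21: 125/365 = 34%. Day 27: 53/365 = 15%. Day 28: 41/365 = 11%. Day 31, the latest day that can be affected: 7/365 = 2%.

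**Effect on the bands (also assumes an onset profile over 0 to 168 days after injection).**

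| Assumed profile | <7 days, true → literal | 7-<28 days, true → literal | Moved from 7-<28 / 28-<56 (points) | Share of 7-<28 band moved |
|---|---|---|---|---|
| Flat | 3.55% → 9.59% | 12.43% → 6.54% | 5.89 / 0.15 | 5.89/12.43 = 47.4% |
| Exponential, mean 28 days | 19.33% → 41.73% | 42.69% → 20.63% | 22.05 / 0.34 | 22.05/42.69 = 51.7% |
| Exponential, mean 14 days | 34.86% → 63.29% | 50.61% → 22.42% | 28.19 / 0.25 | 28.19/50.61 = 55.7% |

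Between 97% and 99% of moves come from the 7-<28 band; for the flat profile, 5.89/(5.89 + 0.15) = 97.5%. With the rule limited to unknown days, no known-date event moves under any profile.

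**The case against.** The best defence is context. The three steps form one item about one variable, and the second and third share the same closing phrase. A missing day is the only thing that needs a substitute; a recorded date does not. On the exception reading all three steps fit together. The literal reading would have the plan discard dates that the protocol takes care to collect. A sensible programmer would probably infer the exception.

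Much of this stands. The exception is very likely what was meant, and on that reading known dates are unaffected. The band shifts belong only to the literal reading. The exponential profiles are illustrations without support in the documents, and even the flat profile assumes equally likely injection dates, whereas Protocol 8.0 lets registration close early once the target is reached. The tables are descriptive, and no test or comparison uses them.

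It does not remove the defect. The limit is inferred, not written, although the SAP writes it in the preceding sentence and again for birth dates. A specific rule that overrides a general formula is ordinary SAP drafting, so a literal programmer would see no contradiction to query. Protocol 10.1 leaves detailed analysis methods to the SAP, so the condition should appear there.

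**Conclusion.** The concern holds. As written, SAP 1.5 replaces known onset dates in the injection month and pushes events towards <7 days in 5.2.1 and 5.2.2. That the condition is missing is certain; that the literal version would be programmed is not.

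Without any assumed onset profile, the literal rule resets between 0 and all 21 of the dates in the 7-<28 day band, depending on the injection date (30-day month). With equally likely injection dates and the three assumed profiles, 47.4% to 55.7% of that band moves. These are worst-case illustrations of the literal reading; the exception reading moves none.

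The damage is confined to the onset bands. AE and ADR counts, incidence and seriousness are the same on both readings. The induration onset item in SAP 5.3.2 would also be affected if 1.5 is applied there, which the SAP does not say. The wording should be corrected, because onset timing is a named item of the surveillance, but it does not threaten the main safety counts.

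**What to change.** Reword the last two sentences of the onset rule in SAP 1.5, for example:

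> If the day of onset is unknown and the event falls in the same calendar month and year as the Leuplin PRO start date, the start date is used. If the day is unknown in any other month, day 1 is used. A known onset date is never replaced.

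Optionally, footnote the number of imputed onset dates in the onset tables. This is useful to readers but is not needed to resolve the ambiguity.

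The cost is one clause. No new data or table is needed, and nothing changes if the programming already follows the exception reading. The rewording protects known dates only; unknown-day events are still imputed as now.
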